Sample size estimates for the intermediate risk group are based on a 50% reduction in the FN rate (the reduction observed in trials for high risk settings). This translates to a reduction in FN rate from 15% to 7.5%, when comparing intermediate risk control arm patients (no PP-CSF) to intermediate risk intervention arm patients (PP-CSF). We believe this is reasonable because the one prospective trial evaluating PP-CSF for intermediate risk chemotherapy given to women with breast cancer achieved a risk reduction of 90%, and a systematic review of clinical trials of PP-CSF use in several settings found an FN rate reduction ranging from 17% to 78%. (49) To account for possible correlation between patients within components we estimate an intraclass correlation coefficient (ICC) of 0.02. An ICC of zero corresponds to randomization of individuals rather than components; $ICC > 0$ indicates patient outcomes are more similar within a component than across components. We estimated the ICC for FN in the SWOG adjuvant breast cancer study **S0221** which has 262 clinics with 2,666 patients. (50) Using a random effects logistic regression program (component is the random effect) followed by numerical integration, the ICC was estimated to be 0.01 although statistically significantly greater than zero. We are using 0.02 to protect against underestimation of the ICC. Based on a two-sided 0.05 alpha level test, 24 components in the Intervention arm (12 components randomized to PP-CSF and 12 components to no PP-CSF among intermediate risk patients) and 45 intermediate-risk patients per component on average will give 80% power to detect whether PP-CSF reduces FN rate by 50% among patients receiving intermediate risk chemotherapy. We assume that high, intermediate and low risk patients comprise 30%, 50% and 20% at each component, respectively; this translates to a total of 90 patients per component on average. (51,52)

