A total of 3,600 eligible patients will be included in the study over a 2.75 year accrual period: 2,160 for the Intervention arm; 720 for the Usual Care arm; and 720 for the Cohort. We will allow for 10% additional accrual for a total of 3,960 patients. On average, this translates to 99 patients per component in the RCT, and 60 patients per component in the Cohort. We will allow the maximum total number of patients per site to be flexible (i.e. not capping accrual at 99 patients per site), in order to allow high-accruing sites to compensate for low-accruing sites, and ultimately allow us to reach our total required sample size of 3,960 patients for the study. This total will account for ineligible patients, as well as dropout and death (not due to FN) that may occur earlier than 6 months after registration and therefore act as a competing event with FN occurrence. Additionally, we will monitor accrual to ensure that our assumed distribution of 30% high, 50% intermediate and 20% low risk patients in the overall sample across all components is roughly maintained. Major deviations from this assumption could result in a loss of power, and therefore if such deviations are observed, we will consider capping accrual by regimen risk.

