accounted for by using mixed effects regression models including a random effect for component. Among high risk and low risk patients, separate mixed effects logistic models will be fit to assess the effect of the intervention on PP-CSF use. In addition to including a random effect for component and an indicator variable for randomized group (Intervention versus Usual Care), we will adjust for component-level characteristics and patient-level clinical and demographic variables.

If the quality of the component application data is acceptable (proportion of missingness $\leq 10\%$), we will descriptively compare trends in PP-CSF prescribing prior to the start of the study versus after the start of the study, in order to determine if there is a change in PP-CSF prescribing at the components based on their participation in the study (i.e., a Hawthorne effect).

b. *Primary Objective b: To compare the rate of febrile neutropenia (FN) between patients registered to Intervention components versus Usual Care components.*

The rate of FN will be evaluated at 6 months post-registration. The risk of FN is greatest during the first cycle, but patients are still at risk throughout therapy. The FN risk levels assigned to the various systemic therapies in this protocol are based on risk for the duration of treatment, and so the analysis will look at the FN rate at 6 months into therapy.

Randomization is at the component level; outcomes are measured at the patient level. Since patients are nested within components, this structure will be accounted for by using mixed effects regression models including a random effect for component. A mixed effects logistic model will be used to assess the effect of the intervention on FN occurrence within 6 months from registration. In addition to including an indicator variable for randomized group (Intervention versus Usual Care), we will adjust for component-level characteristics and patient-level clinical and demographic variables. We will also descriptively compare time to FN occurrence between Intervention and Usual Care practices using Kaplan-Meier plots.

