11.4 Analysis of Additional Objectives

a. *Additional Objective a: To characterize and descriptively report the differences between Cohort components (components with pre-existing guideline-based order entry systems) to the Intervention and Usual Care components, according to the endpoints outlined in [Section 10.0](#).*

Endpoints will be evaluated at the time points described in [Sections 11.2](#) and [11.3](#).

We will characterize and descriptively report all study outcomes in the Cohort components in comparison with the Intervention and Usual Care components. We will evaluate all outcomes, namely adherence to recommendations, clinical outcomes (e.g., FN rates, FN-related hospitalizations) and patient-reported outcomes. As such, this analysis will be exploratory and comparative.

b. *Additional Objective b: To evaluate the time to invasive recurrence in non-metastatic patients by component treatment assignment.*

Patients are followed for 12 months; time to invasive recurrence will be determined by 12 months.

Time from registration to documented invasive local or regional recurrence. Invasive recurrence includes local, regional, or distant recurrence with histological confirmation preferred. Applies only to patients with local or regional disease treated with curative intent. Relapse will not be assessed for persons with metastatic disease at diagnosis. This endpoint will be monitored because it may affect the likelihood of allowing a full dose of systemic therapy, but is not tied to a formal hypothesis because of the small expected number of events. We will summarize this endpoint by calculating cumulative incidence over time.

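### The descriptive Kaplan-Meier plots of time to FN take no account of non-FN death, which the plan itself calls a competing event; cumulative incidence curves would show FN incidence more accurately

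*Combined protocol and SAP*

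**What the plan says.** - **Display (section 11.2, Primary Objective b):** "We will also descriptively compare time to FN occurrence between Intervention and Usual Care practices using Kaplan-Meier plots".
- **Primary test (same section):** "A mixed effects logistic model will be used to assess the effect of the intervention on FN occurrence within 6 months from registration". The plots do not enter the test.
- **Timing of risk (same section):** "The risk of FN is greatest during the first cycle, but patients are still at risk throughout therapy".
- **Competing event (section 11.1):** the allowance for extra accrual covers ineligibility and dropout. It also covers "death (not due to FN) that may occur earlier than 6 months after registration and therefore act as a competing event with FN occurrence". The only provision attached to it is the accrual itself: "We will allow for 10% additional accrual for a total of 3,960 patients".
- **Another time-to-event endpoint (section 11.4, Additional Objective b, invasive recurrence):** "We will summarize this endpoint by calculating cumulative incidence over time". Neither an estimator nor a competing event is named there.
- **Missing outcomes (section 11.6):** a patient whose FN outcome stays missing is scored as having no FN.
- **Censoring:** section 10.1 has a censoring sentence for overall survival. None is given for time to FN.

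**The concern.** Kaplan-Meier with deaths censored treats a patient who died without FN as if that patient could still develop FN later at the same rate as the survivors. The complement of the curve then estimates FN risk in a setting without other deaths, and it lies above the share of patients who actually have FN. Section 5.1 admits metastatic disease, so some early non-FN deaths are plausible, and section 11.1 expects them.

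What is at stake is how one figure is read. The primary endpoint counts FN by 6 months among all patients, with a patient who dies without FN counted as no FN. A reader who takes the 6-month FN rate from the plotted curve would get a slightly higher number than the crude proportion behind the primary analysis.

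**Working it through.** **1. The plan's own allowance.** 32 components × 90 + 720 cohort patients = 3,600, and 3,600 × 1.10 = 3,960, which reproduces section 11.1. Extra accrual replaces lost patients but does not change what a Kaplan-Meier curve estimates.

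**2. Inputs.**
- 6-month FN rate without PP-CSF at intermediate risk: 15% (section 11.1).
- Non-FN death by 6 months, D: not in the documents; 5-15% assumed.
- FN hazard: half of the 6-month cumulative hazard in month 1, the rest spread evenly over months 2-6. This is an assumption in line with the plan's statement that risk peaks in cycle 1.
- Death hazard constant; deaths without FN censored in the Kaplan-Meier estimate (assumed, since the plan states no rule).

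**3. Formulas, time in months.** With 1-KM = F:
- H = −ln(1 − F), h₁ = 0.5H, h₂ = 0.5H/5, g = −ln(1 − D)/6
- Cumulative incidence = h₁/(h₁+g) × [1 − e^−(h₁+g)] + e^−(h₁+g) × h₂/(h₂+g) × [1 − e^−5(h₂+g)]

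**4. Numbers for F = 15%.** H = 0.1625, h₁ = 0.0813, h₂ = 0.0163.
- D = 5%: g = 0.00855. Cumulative incidence = 0.0777 + 0.9141 × 0.0764 = 0.1476. Gap 15.00 − 14.76 = 0.24 points.
- D = 15%: g = 0.02709. Cumulative incidence = 0.0770 + 0.8973 × 0.0731 = 0.1426. Gap 15.00 − 14.26 = 0.74 points.

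**5. Other hazard splits, F = 15%.** Only the month-1 share changes.

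| Share of FN hazard in month 1 | Gap, D = 5% | Gap, D = 15% |
|---|---|---|
| 70% | 0.17 | 0.52 |
| 50% | 0.24 | 0.74 |
| One sixth (uniform) | 0.37 | 1.13 |

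The more FN is concentrated early, the smaller the gap.

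**6. Effect on the comparison.** Pooling high and intermediate risk gives (0.30 × 25% + 0.50 × 15%)/0.80 = 18.75% in Usual Care, and half of that, 9.375%, in Intervention. Here the true incidence is held at these values and 1-KM is computed, with 11.5% (uniform), 50% or 70% of the FN hazard in the first 21 of 182 days. With 10% deaths in both arms, 1-KM reads 19.1-19.7% and 9.6-9.9%. In the runs made at equal mortality (2-20% deaths, uniform and 50% splits) the ratio of the two curves stays at 0.50. If deaths were 10% in Usual Care and 5% in Intervention (an illustration only), the ratio would be 0.49 and the difference 9.8-10.1 points instead of 9.4 (uniform and 50% splits).

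**The case against.** The strongest reply is that nothing depends on this plot. It is labelled descriptive, and no test, interim boundary (section 11.9) or sample size uses it. That stands, and it makes this a minor point.

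Second, the bias is conditional. The plan states no censoring rule for FN. If patients who die without FN were kept at risk as FN-free to 6 months, then apart from other censoring 1-KM at 6 months would equal the crude proportion. So a reader might infer that the curves are certain to overstate FN, but the documents support this only under the usual convention.

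Third, a reader might infer that switching estimator makes the figure agree exactly with the primary analysis. It does not. The primary model is covariate-adjusted with a component random effect, and section 11.6 scores missing outcomes as zero, whereas a cumulative incidence curve would censor dropouts.

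Fourth, a reader might apply the gap at 25% FN to metastatic lung cancer; with 15% mortality and the half-in-month-1 split it is 1.2 points (25.0% against 23.8%). Table 3 in section 18.1 does not support that pairing: every High-risk regimen listed is a breast regimen, and lung and colorectal regimens are Low or Intermediate. The 15% case is the relevant ceiling for lung.

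Fifth, a reader might infer bias that differs between arms. No section suggests that early non-FN mortality differs by arm.

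Lastly, section 11.1 uses the competing-event wording loosely, to justify accrual, and puts dropout in the same clause. Dropout is ordinary censoring. For death, the description is correct and the choice of curve should follow it.

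**Conclusion.** The point holds as a minor, conditional one. The plan recognises non-FN death as a competing event and then names a display that, as usually computed, ignores it. At 15% FN the overstatement at 6 months is about 0.2-0.7 points with half the FN hazard in month 1, and about 0.2-1.1 across the other splits tried. This rests on three assumptions the documents do not settle: 5-15% non-FN mortality by 6 months, the hazard split over time, and censoring of deaths without FN. Objective b's logistic analysis, the power and the interim rules do not change. With equal mortality in both arms the relative contrast is also essentially unchanged.

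**What to change.** In section 11.2, Primary Objective b, replace the Kaplan-Meier plots with Aalen-Johansen cumulative incidence curves of FN by arm, with death without FN as the competing event and loss to follow-up censored. A footnote to the figure should say that missing outcomes are scored as zero in the primary analysis (section 11.6), so that small remaining differences are understood.

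If Kaplan-Meier is kept, state how deaths without FN are handled. If they are censored, label the curve as FN risk in the absence of other deaths.

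The cost is one or two sentences. Notice of Death and the Cause of Death Supplement are already collected (sections 9.0 and 14.4), and the 6 Month FN Log is already required when a patient dies before 6 months (section 14.4). No test, sample size or data collection changes.

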11.3 Analysis of Secondary Objectives

- a. *Secondary Objective a: To compare the rate of FN between low-risk patients registered at Intervention components versus Usual Care components.*

The rate of FN will be evaluated at 6 months post-registration. The risk of FN is greatest during the first cycle, but patients are still at risk throughout therapy. The FN risk levels assigned to the various systemic therapies in this protocol are based on risk for the duration of treatment, and so the analysis will look at the FN rate at 6 months into therapy.

A mixed effects logistic model with a random effect for component will be used to assess the effect of prescribing CSFs as primary prophylaxis on FN occurrence within 6 months from registration among low-risk patients. In addition to including an indicator variable for component assignment (Intervention versus Usual Care), we will adjust for component-level characteristics and patient-level clinical and demographic variables.

- b. *Secondary Objective b: To compare the FN-related health-related quality of life (HRQL) between low-risk patients registered at Intervention components versus Usual Care components.*

HRQL is evaluated at the end of the first cycle, the target period for the intervention, while accounting for baseline.

A linear mixed effects model will be fit to assess the effect of the intervention on HRQL, treating the FACT-N score at the follow-up clinic visit as the outcome and adjusting for the baseline FACT-N score. In addition to including an indicator variable for randomized group and a random effect for component, we will adjust for component-level characteristics and patient-level clinical and demographic variables.

- c. *Secondary Objective c: To compare patient adherence to PP-CSF prescribing between patients registered at Intervention components versus Usual Care components.*

PP-CSF is only prescribed during the first cycle, so patient adherence to PP-CSF will be evaluated during the first cycle.

For the home and clinic settings, separate mixed effects logistic models will be used to assess the effect of the intervention on adherence to PP-CSF orders, treating adherence after the start of the study as the outcome. In addition to including an indicator variable for randomized group and a random effect for component, we will adjust for component-level characteristics and patient-level clinical and demographic variables.

d. *Secondary Objective d: To compare patient knowledge of the indications for, efficacy of, and side effects associated with PP-CSF between the initiation and conclusion of the first cycle of myelosuppressive systemic therapy between patients registered at Intervention components versus Usual Care components.*

PP-CSF is only prescribed during the first cycle, so patient knowledge of PP-CSF will be evaluated as the change in knowledge between baseline and the end of the first cycle.

We will analyze change in the patient knowledge score between the initiation and conclusion of the first cycle of myelosuppressive systemic therapy, by fitting a linear mixed effects model with a time variable and an interaction between randomized group and time. We will use random effects to accommodate both the correlation among measures from the same patient as well as the correlation among patients from the same component. We will also adjust for component-level characteristics and patient-level clinical and demographic variables.

e. *Secondary Objective e: To compare the proportion of patients completing the initial systemic therapy regimen at planned duration and at planned dose intensity between patients registered at Intervention components versus Usual Care components.*

Patients are followed for 12 months; therapy status will be determined by 12 months.

Two separate mixed effects logistic models will be used to assess the effect of the intervention on completion of the initial systemic therapy regimen (i) at planned duration and (ii) at planned dose intensity. In addition to including an indicator variable for randomized group and a random effect for component, we will adjust for component- level characteristics and patient-level clinical and demographic variables.

f. *Secondary Objective f: To compare antibiotic use both as prophylaxis and as treatment for FN between patients registered at Intervention components versus Usual Care components.*

Antibiotic use as prophylaxis for FN and as a treatment for FN is relevant during the first cycle when PP-CSF may be administered. To adequately cover all antibiotic use that may be related to prophylaxis and treatment of FN, antibiotic prescriptions for the first 30 days of systemic treatment will be evaluated.

A linear mixed effects model will be fit to assess the effect of the intervention on duration of antibiotics use with number of days as the outcome. Mixed effects Poisson models will be used to assess the effect of the intervention on total number of antibiotics agents used. Three separate models will be fit, with the following outcomes: (i) the number of times antibiotics were used as prophylaxis, (ii) the number of times antibiotics were used as treatment for FN, and (iii) the

total number of times antibiotics were used. In addition to including an indicator variable for randomized group and a random effect for component, we will adjust for component-level characteristics and patient-level clinical and demographic variables. Robust variance estimation will be used to relax the strong assumptions about the variance made by Poisson regression. If a large number of zero counts is observed, then zero-inflated Poisson regression will be used.

g. *Secondary Objective g: To compare the rate of FN-related emergency department visits and hospitalizations among intermediate risk patients registered to Intervention components by component treatment assignment (administer PP-CSF to intermediate risk patients versus not).*

Hospitalizations and ED visits will be evaluated at the end of the first cycle, when patients are at greatest risk for FN and thus more likely to have a hospitalization and/or ED visit for FN.

A mixed effects Poisson model will be used to assess the effect of the intervention on FN-related ED visits and hospitalizations, stated as a composite endpoint because some patients are directly admitted from clinic to hospital, bypassing the ED. In addition to including an indicator variable for randomized group and a random effect for component, we will adjust for component-level characteristics and patient-level clinical and demographic variables. We will account for variable lengths of follow-up across patients due to varying lengths of the initial regimen by including an offset term in the model. Robust variance estimation will be used to relax the strong assumptions about the variance made by Poisson regression. If a large number of zero counts is observed, then zero-inflated Poisson regression will be used.

h. *Secondary Objective h: To compare the FN-related health-related quality of life (HRQL) patients among intermediate risk patients registered to Intervention components by component treatment assignment (administer PP-CSF to intermediate risk patients versus not).*

HRQL is evaluated at the end of the first cycle, the target period for the intervention, while accounting for baseline.

A linear mixed effects model will be fit to assess the effect of the intervention on HRQL, treating the FACT-N score at the follow-up clinic visit as the outcome and adjusting for the baseline FACT-N score. In addition to including an indicator variable for randomized group and a random effect for component, we will adjust for component-level characteristics and patient-level clinical and demographic variables

i. *Secondary Objective i: To compare overall survival among intermediate risk patients registered to Intervention components by component treatment assignment (administer PP-CSF to intermediate risk patients versus not).*

Patients are followed for 12 months; survival status will be determined by 12 months.

A Cox proportional hazards model will be used to model survival. The outcome will be overall survival measured in days since trial entry to 1 year following entry. In addition to including an indicator variable for randomized group, we will adjust for component-level characteristics and patient-level clinical and demographic variables. A separate analysis of cause-specific survival to address FN-related deaths will also be conducted.

11.4 Analysis of Additional Objectives

a. *Additional Objective a: To characterize and descriptively report the differences between Cohort components (components with pre-existing guideline-based order entry systems) to the Intervention and Usual Care components, according to the endpoints outlined in [Section 10.0](#).*

Endpoints will be evaluated at the time points described in [Sections 11.2](#) and [11.3](#).

We will characterize and descriptively report all study outcomes in the Cohort components in comparison with the Intervention and Usual Care components. We will evaluate all outcomes, namely adherence to recommendations, clinical outcomes (e.g., FN rates, FN-related hospitalizations) and patient-reported outcomes. As such, this analysis will be exploratory and comparative.

b. *Additional Objective b: To evaluate the time to invasive recurrence in non-metastatic patients by component treatment assignment.*

Patients are followed for 12 months; time to invasive recurrence will be determined by 12 months.

Time from registration to documented invasive local or regional recurrence. Invasive recurrence includes local, regional, or distant recurrence with histological confirmation preferred. Applies only to patients with local or regional disease treated with curative intent. Relapse will not be assessed for persons with metastatic disease at diagnosis. This endpoint will be monitored because it may affect the likelihood of allowing a full dose of systemic therapy, but is not tied to a formal hypothesis because of the small expected number of events. We will summarize this endpoint by calculating cumulative incidence over time.

